4 STUDY DESIGN

This is an open-label, non-placebo controlled pharmacokinetic (PK) assessment study. The study will consist of six-procedure days (10 subjects) with at least two weeks between procedure days. The half-life of fentanyl is approximately 24 hours. Hence, 7 days (i.e. 5 half-lives) will be sufficient for >95% of fentanyl to be eliminated from the body. Each of the 10 subjects will be enrolled to complete all six procedure days (Procedure Days 1 to 6). The study is open label and not blinded, because PK assessment is not subject to participant and/or observer bias. After each procedure session (procedure day) is completed, the available safety data will be reviewed by an Independent Safety Monitor (ISM) to determine whether or not to proceed to the next procedure day.

The six procedures days are as follows:

Procedure Day 1: An **Apotex** (fentanyl) patch will be applied without heat for 11 hours, then a theratherm® heating pad will be applied over it (see details in Manual of Procedures) and set to induce a skin temperature of $42.0 \pm 2^{\circ}$ C for 1 hour then removed, and the patch will be kept on for another 7 hours (patch will be applied for a total of 19 hours), then it will be removed. Each subject will receive a naltrexone hydrochloride 50 mg oral tablet 12 ± 1 hour and shortly prior to patch application and then every 12 ± 1 hour for 8 additional doses, then one dose every 24 ± 2 hours for two more doses. A total of twelve 50 mg oral doses of naltrexone will be administered.

Procedure Day 2: An **Apotex** (fentanyl) patch will be applied without heat for 18 hours, then a theratherm® heating pad will be applied over it and set to induce a skin temperature of $42.0 \pm 2^{\circ}$ C for 1 hour, then the patch and the heating pad will both be removed (patch will be applied for a total of 19 hours). Each subject will receive a naltrexone hydrochloride 50 mg oral tablet 12 \pm 1 hour and shortly prior to patch application and then every 12 ± 1 hour for 8 additional doses, then one dose every 24 ± 2 hours for two more doses. A total of twelve 50 mg oral doses of naltrexone will be administered.

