7.2 Pharmacokinetics (PK) Analyses

Fentanyl concentrations will be measured in serum samples collected from each subject from the opposite arm to which the fentanyl system will be applied. Blood samples (approximately 5 mL) will be collected during each procedure day, 15 min before patch application and then at 1:00, 10:00, 10:55, 11:05, 11:15, 11:25, 11:35, 11:45, 12:00, 13:00, 14:00, 16:00, 17:00, 17:55, 18:05, 18:15, 18:25, 18:35, 18:45, 19:00 20:00, 21:00 and 22:00 hr post-patch application. The fentanyl PK parameters to be estimated using non-compartmental analysis (NCA) after each system application are: maximum serum concentration (Cmax) at different time intervals; 0-11, 0-19, 0-22, 11-12, 12-18, 18-19 and 19-22 hr; apparent elimination rate constant (k); apparent half-life (t1/2), calculated as 0.693/k; AUC of the serum concentration–time at different time intervals; 0-11, 0-19, 0-22, 11-12, 12-18, 18-19 and 19-22 hr determined by the linear trapezoidal method; and AUC value extrapolated to infinity (AUCinf), calculated as the sum of AUC₂₂ and the area extrapolated to infinity: AUCinf = AUC₂₂ + C₂₂/k where C₂₂ would be the last quantifiable concentration. All NCA analyses will be conducted using Phoenix® WinNonlin[®] 6.3 (Pharsight, a Certara Company, CA).

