7.3 Final Analysis Plan

The main objective of this study is to investigate the influence of heat application on the PK parameters of fentanyl after using reference and generic patch products. The primary PK parameters to be compared are 1) Cmax, before and after heat application and 2) AUC before and after heat application consistent with similar PK studies [4, 5, 7, 8, 16-22]. Analysis of variance (ANOVA) followed by post-hoc Bonferroni test will be used for comparing the differences in the means of the PK parameters and significant differences will be declared at p < 0.05. The statistical comparisons will be conducted as follow:

Three pair-wise comparisons between the patches (Apotex v Mylan; Apotex v Duragesic[®]; and Mylan v Duragesic[®]) will be performed using the results of a three-way repeated-measures ANOVA. The model will include time, type of patch (e.g., Apotex or Mylan), application of heat (yes or no), and interaction between patch and application of heat. The time term comprises multiple indicator variables for maximum model flexibility to perform the comparison at different time points specified above. We will test the null hypothesis that the coefficient for the patch-by-heat interaction equals zero, adjusting for time.

If fentanyl concentrations are found to be non-normally distributed, then we will examine Box-Cox transformations (e.g., log, square-root, etc.) that can achieve normality. If no transformation can achieve normality, then we will use permutation tests to compute empirical p-values, and we will use the bootstrap to compute standard errors and confidence intervals that account for within-person correlation.

A secondary analysis will assess the effects of heat and time on fentanyl within a patch. Specifically, the ANOVA will also include interaction terms of time with patch and heat, and a three-way interaction between time, heat, and patch. Inclusion of the three-way term allows the effects of heat on fentanyl to differ by patch. Testing the time-by-heat interaction, separately for each patch, using the same procedure outlined above produces estimates of intra-procedure effects.

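### Fitted to all listed draws, the primary patch-by-heat model includes near-zero early samples that turn a plain level difference between products into an apparent heat interaction

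*Combined protocol and SAP*

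**What the plan says.** All references are to the combined protocol and SAP unless stated.

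- **Primary test (7.1, 7.3).** The question is whether heat affects serum concentrations differently by product, tested by the patch-by-heat coefficient adjusted for time. The model has time, patch, heat (yes or no) and patch-by-heat. On time: "The time term comprises multiple indicator variables for maximum model flexibility to perform the comparison at different time points specified above". Patch-by-time appears only in the secondary analysis. The threshold is "significant differences will be declared at p < 0.05", with Bonferroni post-hoc tests.
- **Draws (7.2).** "Blood samples (approximately 5 mL) will be collected during each procedure day, 15 min before patch application and then at 1:00, 10:00", followed by 21 further times up to 22:00, so 24 draws per session.
- **Non-normality (7.3).** "If fentanyl concentrations are found to be non-normally distributed, then we will examine Box-Cox transformations (e.g., log, square-root, etc.) that can achieve normality". Should every transformation fail, permutation tests and the bootstrap follow.
- **Design (section 4).** "Each of the 10 subjects will be enrolled to complete all six procedure days", "with at least two weeks between procedure days". Heat is on at 11-12 h or at 18-19 h.
- **Level difference.** The SAP's list of pharmacokinetic parameters gives absolute bioavailability of 0.36 for Duragesic and 0.42 for Mylan.

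The supplied text has no rule for zero or unquantifiable concentrations in this model, does not say whether the pre-patch draw enters it, and does not define heat draw by draw. Section 7.3 also names Cmax and AUC as the primary parameters.

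**The concern.** The study exists to say whether generic patches respond to heat differently from the reference. A product that simply delivers more, by the same ratio at all times and with the same response to heat, should not be declared more heat-sensitive.

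With one patch term for all times, the model expects the product difference to be the same at every draw, apart from heat. It cannot be the same before the patch is on, when all products are at zero, and on the raw and square-root scales it is also compressed at 1:00. Both draws are always in the unheated group, so they pull down the unheated product difference. The shortfall appears as a larger difference under heat, which is the coefficient being tested. Neither draw says anything about heat, because no pad is on before 11 h.

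**Working it through.** **1. Is the pre-patch value effectively zero?** The documents do not say so directly; it follows from the washout. Section 4 gives "The half-life of fentanyl is approximately 24 hours" and "Hence, 7 days (i.e. 5 half-lives) will be sufficient for >95% of fentanyl to be eliminated from the body". Eliminated share = 1 − 0.5^(time/half-life). Five half-lives give 96.9%; 7 days at 24 h is seven half-lives, or 99.2%. The >95% therefore reproduces, although 7 days equals five half-lives only at 33.6 h. At 14 days the residual is 0.5^14 = 0.006% (24 h) or 0.5^10 = 0.1% (33.6 h). So 10 × 6 = 60 of 60 × 24 = 1,440 planned draws (4.2%) are effectively zero.

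**2. Log-scale leak from the pre-patch draw.** Take two products with a constant log gap g and the same heat response, so the true interaction is 0. The design is the same for both, so time and common heat effects cancel in the product difference D. Least squares then gives: interaction = mean D over heated draws − mean D over unheated draws. D = g everywhere, except 0 at the pre-patch draw when a common constant is entered.

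| Heat = yes | Heated draws (early + late session) | Unheated draws | Pre-patch among them | Interaction |
|---|---|---|---|---|
| Pad on | 6 + 6 = 12 | 36 | 2 | g − (34/36)g = g/18 = 5.6% of g |
| From onset onward | 20 + 9 = 29 | 19 | 2 | g − (17/19)g = 2g/19 = 10.5% of g |

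The constant cancels, so its value does not matter. If 1:00 were unquantifiable for every product as well, the shares double to 4/36 = 11.1% and 4/19 = 21.1%. Without the pre-patch draw, and with no other value substituted, the interaction is exactly 0.

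**3. Size as a false ratio of heat effects, exp(share × g), pre-patch draw only.**

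| Level ratio | g | Pad on | From onset |
|---|---|---|---|
| 0.42/0.36 = 1.167 | 0.154 | 1.009 | 1.016 |
| 1.5 (assumed) | 0.405 | 1.023 | 1.044 |

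**4. Raw and square-root scales.** No substitution is needed, because the difference between products is itself zero before the patch. Noiseless fit, assuming one compartment, zero-order input for 19 h, steady state 0.6 ng/mL, input × 1.5 during the heated hour, level ratio 1.5 and heat = pad on:

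| Scale, half-life | All 24 draws | From 10:00 |
|---|---|---|
| Square root, 24 h | 0.0096 | −0.0003 |
| Square root, 8 h | 0.0157 | 0.0022 |
| Raw, 24 h | 0.0109 | −0.0005 |
| Raw, 8 h | 0.0290 | 0.0065 |

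The restriction removes between 1 − 0.0065/0.0290 = 78% and 1 − 0.0003/0.0096 = 97%.

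**5. Simulated false-positive rate.** Ten subjects; the kinetics of step 4 with half-life 24 h, 8 h, or 24 h with a 2 h absorption lag; log SDs of 0.35 (subject), 0.15 (session) and 0.10 (assay); quantification limit 0.02 ng/mL with half substituted on the log scale; heat = pad on; unadjusted paired t-test per pair at two-sided 0.05. All of these are assumptions except the 24 h half-life, the number of subjects and the 0.05.

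| Level ratio | Draws | Rate |
|---|---|---|
| 1.167 | All | about 6%-17% across scales |
| 1.5 | All | raw 36%-68%; square root 51%-63%; log 17%-75% |
| 1.5 | From 10:00 | 5%-9% |

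On the log scale, with no level gap the rate stays near 5% whichever draws are used.

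**The case against.** **The plan does not say that this model will be run on these draws.** Section 7.3 also names Cmax and AUC, for which a pre-patch zero is never a response. This stands as an ambiguity. Section 7.1 and the transformation sentence both speak of concentrations, and the time indicators point to the listed draws, so the draw-level reading is natural but not certain.

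**A reader might infer that the planned remedy cannot score the draw at all.** It can: square root takes a zero, and so does the permutation fallback. Only log, and Box-Cox powers at or below zero, fail. This does not remove the problem, because the leak occurs on the square-root and raw scales without any substitution.

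**A reader might infer that the answer depends on an arbitrary substituted value.** For the pre-patch draw it does not; the time indicator absorbs the constant. The value matters only if 1:00 straddles the quantification limit, which the documents do not give. In one such assumed case (24 h half-life, 1.3-fold gap) the false interaction changed sign, to −0.015.

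**The large error rates are assumption-driven.** Correct. Gaps of 1.3 and 1.5 have no source, and the highest log-scale rates come from the added lag. The test was unadjusted. On the log scale, three-pair Bonferroni at a 1.3-fold gap without lag gives 4%-6% per pair against a nominal 1.7%. The plan does not state the error term: a pooled residual with subject effects gives 0.3%-2% at gaps of 1.3 and 1.5 without lag, and 6% and 23% with it.

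**The secondary model adds patch-by-time terms and would absorb the mismatch.** True, but the primary hypothesis is tested without them.

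**Dropping unquantifiable values would also work.** On the log scale, largely: 4%-7% in the same kind of simulation. The supplied text specifies neither option. The protocol cites a Manual of Procedures that was not among the documents.

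**Conclusion.** The point holds conditionally. If the primary model is fitted to concentrations at all listed times, a constant level difference leaks into the tested coefficient on the raw and square-root scales, and on the log scale when a constant is entered for the zero. The log-scale shares of 5.6% and 10.5% follow from the sampling schedule and the stated model terms, without kinetic assumptions.

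At the only level ratio the documents supply, the effect is modest: a false heat ratio of about 1.01 to 1.02 from the pre-patch draw, and about 6% to 17% unadjusted false positives against 5% with all draws. Using bioavailability as the level gap is itself an assumption. Even so, 1% to 2% is not negligible here: under the assumed kinetics, the model's own common heat coefficient is only 0.007 to 0.015 on the log scale, which is of the same order.

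A reader might take the rates of up to about 70% as the trial's error rate. The documents do not support that; those rates need assumed gaps of 1.3 to 1.5, depend on the assumed variances, lag and error term, and are before Bonferroni.

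**What to change.** In 7.3, state that the patch-by-heat concentration model, and the normality and Box-Cox checks that go with it, use only draws from 10:00 onward, with no substituted values. Keep the pre-patch and 1:00 draws for the non-compartmental AUCs and as a check on carry-over.

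This removes the leak on the log scale. On the raw and square-root scales it removes most of it with heat = pad on; some remains, more so if heat is coded from onset onward, because the primary model has no patch-by-time term.

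The cost is one sentence, and two time points that are always unheated leave the model. No heat contrast is lost, and sampling does not change.

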DETERMINATION OF SERUM FENTANYL LEVELS AFTER USING REFERENCE AND GENERIC TRANSDERMAL FENTANYL PATCHES WITH AND WITHOUT STANDARDIZED HEAT APPLICATION IN HEALTHY HUMAN VOLUNTEERS

Short title: The Effect of Heat on Fentanyl Release from Fentanyl Patches in Healthy Adults

Clinical Protocol Principal Investigator:

[name], MS

U01 Principal Investigator(s):

[name] (contact), PhD

[name]

Sponsor:

Food and Drug Administration

Grant Number: 1U01FD004955-01

Version 8.0

12 June 2017

STATEMENT OF COMPLIANCE

This study will be conducted in compliance with the protocol, International Conference on Harmonisation Good Clinical Practice E6 (ICH-GCP) and the applicable Food and Drug Administration and other Department of Health and Human Services regulatory requirements.

All key personnel (all individuals responsible for the design and conduct of this study) have completed Human Subjects Protection Training.

PROTOCOL SUMMARY

Title:	Determination of Serum Fentanyl Levels after using Reference and Generic Transdermal Fentanyl Patches with and without Standardized Heat Application in Healthy Human Volunteers	
Population:	Healthy adults age 18 – 45 years	
Number of Sites:	Single site: University of Maryland School of Medicine	
Study Duration:	Approximately 18 weeks including the screening period	
Subject Participation Duration:	Approximately 12 weeks including the screening period	
Description of Study Product:	Fentanyl (Duragesic [®] , matrix type, Janssen Pharmaceutics; Mylan (fentanyl) matrix type, Mylan Pharmaceuticals and Apotex (fentanyl) matrix type, Apotex Corp.) transdermal patches, and naltrexone hydrochloride tablet and naloxone hydrochloride injections	
Objective:	To determine serum fentanyl levels after using reference (Duragesic [®]) and generic fentanyl (Mylan and Apotex) transdermal patches with and without standardized heat application in healthy adult volunteers	
Description of Study Design:	The study will be an open-label, study with six procedure days (n=10 healthy subjects completing all 6 procedure days) with at least two weeks between each procedure day and the subsequent one.	
	Each of the 10 subjects will be enrolled to complete all six procedure days. For each of the fentanyl products ($n=3$) there will be two procedure days, and on all procedure days the patches will be applied for 19 hours.	
	The study will contain six procedure days:	

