5 STUDY ENROLLMENT AND WITHDRAWAL

Only adult subjects who meet the inclusion/exclusion criteria will be eligible for enrollment into this study. Ten subjects will be recruited, and five alternates who could replace subjects who drop out from the study for any unforeseen reason. The study population selected for this study includes healthy adult men and women ages 18 to 45, inclusive. The selection criteria are designed to exclude persons who might have medical conditions that could pose a safety risk and persons whose medical conditions might interfere with the objectives and results of the study.

Subjects may be recruited from the databases at the Center for Vaccine Development (CVD), by referral from another healthcare professional, and by advertisements local to the study center. Potential subjects who are interested in the study will be informed of the study and if they wish to participate, will receive additional study information, including an informed consent form. Each of the 10 subjects enrolled will be expected to complete the 6 procedure day sessions.

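### If the section 7.3 fallback is used, ordinary bootstrap standard errors and intervals over 10 subjects are too narrow: nominal 95% limits cover about 90%

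*Combined protocol and SAP*

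**What the plan says.** Section 7.3 of the combined protocol and SAP plans a repeated-measures analysis: "Analysis of variance (ANOVA) followed by post-hoc Bonferroni test will be used", and "significant differences will be declared at p < 0.05". The comparisons are described as "Three pair-wise comparisons between the patches". If the concentrations are not normal, Box-Cox transformations are tried first. Only after those fail does the fallback apply, and it has two parts:

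- Testing: "If no transformation can achieve normality, then we will use permutation tests to compute empirical p-values".
- Estimation: "we will use the bootstrap to compute standard errors and confidence intervals that account for within-person correlation".

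The Protocol Summary gives the sample as "n=10 healthy subjects completing all 6 procedure days". Section 5 adds: "Ten subjects will be recruited, and five alternates who could replace subjects who drop out from the study for any unforeseen reason". So the number of complete subjects stays at 10 if replacement succeeds.

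Section 7.3 does not give the bootstrap type, the resampling unit, the number of resamples, the confidence level or the permutation scheme.

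**The concern.** A bootstrap that respects within-person correlation has to resample whole subjects, however many blood samples each one gives. With 10 units, two small-sample corrections are lost. The bootstrap variance of a mean divides by n instead of n - 1. The usual limits also use normal or percentile cut-offs where a t distribution with 9 degrees of freedom is needed. Both errors shorten the interval.

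At stake is how the differences between patches in the heat effect are reported, which is the trial's primary question. In the fallback the stated uncertainty would be too small. The report could also show an interval that excludes zero next to a permutation p-value that is not significant, and the plan gives no rule for reading that conflict.

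**Working it through.** The documents give no coverage figure to reproduce, so the check starts from their inputs.

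**Inputs.** n = 10 subjects (section 4); alpha = 0.05 and three patch pairs with Bonferroni (section 7.3). Derived: 0.05/3 = 0.0167, hence 98.33% intervals. Assumed: two-sided level, the subject as resampling unit, 10 complete subjects, and one summary contrast per subject and patch pair.

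**Standard error.** Bootstrap SE / usual SE = sqrt(9/10) = 0.949, about 5% too small.

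**Closed form, normal contrasts.** A normal-type interval with the bootstrap SE covers with probability P(|t9| < z × sqrt(0.9)).

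- Nominal 95%: 1.960 × 0.949 = 1.859. Coverage is 90.4%, so non-coverage is 9.6% against 5%. Width relative to the t interval: 1.859/2.262 = 0.82.
- Nominal 98.33%: 2.394 × 0.949 = 2.271. Coverage is 95.1%, so non-coverage is 4.9% against 1.67%, a ratio of 2.96. Relative width: 2.271/2.933 = 0.77.

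A contrast whose t statistic lies between 1.86 and 2.26 (nominal 95%), or between 2.27 and 2.93 (nominal 98.33%), would have a bootstrap interval that excludes zero although the 9-df t test is not significant.

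**Simulation.** Subject-level bootstrap, 6,000 data sets, 1,999 resamples. Non-coverage in %, at nominal 5% / nominal 1.67%:

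| Contrast distribution | Percentile | Normal-type | Bootstrap-t | 9-df t |
|---|---|---|---|---|
| Normal | 9.37 / 4.93 | 8.88 / 4.43 | 4.52 / 1.75 | 4.50 / 1.65 |
| t with 3 df | 11.70 / 6.43 | 9.03 / 4.43 | 8.00 / 2.93 | 4.42 / 1.25 |
| Difference of lognormals, log-SD 0.5 | 10.80 / 5.92 | 9.35 / 4.45 | 6.73 / 2.17 | 4.55 / 1.05 |
| Difference of lognormals, log-SD 1 | 11.65 / 6.70 | 7.68 / 2.90 | 8.75 / 2.58 | 2.88 / 0.47 |

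A separate run gave percentile misses of 9.5-12.5% and 5.1-7.1% for normal and symmetric heavy-tailed contrasts. Percentile limits therefore cover about 87-91% at nominal 95% and 93-95% at nominal 98.33%. Normal-type limits do slightly better with heavy tails. BCa limits are no remedy: they miss 9.67% at nominal 5% for normal contrasts.

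**The permutation side.** In 4,000 simulated three-patch data sets, an exact sign-flip test of whole-subject contrasts at 0.05/3 gave 1.5-1.7% error per comparison and 4.1-4.7% over the three. Ten subjects give 2^10 = 1,024 sign patterns. The smallest two-sided p is 2/1,024 = 0.002, and the largest attainable level not above 0.0167 is 16/1,024 = 0.0156, so the test can reach the Bonferroni level.

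**The case against.** **The false-positive rate.** A reader might infer that the plan roughly triples its rate of false claims about patches. The documents do not support that: in the fallback, significance comes from permutation p-values. If decisions were instead read from percentile intervals at 0.05/3, the family-wise error would be 12.9-16.1% in simulation, but that rule is not in the plan. This objection stands.

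**The bootstrap type.** It is not named, and bootstrap-t is close to nominal for normal contrasts. The figures do depend on assuming an ordinary bootstrap. But nothing in section 7.3 points to bootstrap-t, the section promises standard errors as well as intervals, and bootstrap-t misses 6.7-8.8% at nominal 5% with the heavy tails that could trigger the fallback.

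**The permutation test.** It is also tempting to call it unsound because clock time fixes heat status. That holds only within a day. Section 4 heats each patch at 11-12 h on one day and at 18-19 h on another, so the same subject is seen heated and unheated at the same clock time. What remains is that the permutation unit is unstated. Section 7.3 does not say that single records would be shuffled, but it does not rule it out.

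**The replacement methods.** They can fail too. If the contrasts themselves are strongly skewed, the 9-df t interval misses about 10% (exponential) to 16-17% (lognormal, log-SD 1) at nominal 5%, and the sign-flip test also exceeds its level. This limits the fix without defeating it. A between-patch difference is symmetric under the null if the patches are exchangeable within a subject. For symmetric contrasts the sign-flip test rejected 4.5-5.4% and the t interval missed 3.0-4.7%. Exchangeability is an assumption here, since the available text describes no randomised order.

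**Reach.** This is a last-resort clause, and the documents do not show how likely it is to be used.

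**Conclusion.** The point holds for the fallback's standard errors and confidence intervals. With 10 subjects, an ordinary bootstrap SE is about 5% too small. Coverage is about 90% at nominal 95% and about 95% at nominal 98.33%, falling to about 93% for percentile limits with heavy tails. The consequence is overstated precision and possible conflict with the permutation p-value, not an inflated error rate for the planned test.

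The conclusion rests on a percentile or normal-type bootstrap, the subject as unit, a two-sided level, 10 complete subjects, and a confidence level inferred from p < 0.05 and Bonferroni over three pairs. It matters only if the fallback is reached. It should still be corrected in advance, because a better interval is available at almost no cost.

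**What to change.** Amend the fallback in section 7.3 as follows.

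1. For each subject and patch, compute the heat effect on the chosen PK parameter by comparing the early-heat and late-heat days at the same clock time. The 11-12 h window gives a heated versus not-yet-heated comparison. At 18-19 h the comparison day has already been heated, and the text should say how that is handled.
2. For each patch pair, take the within-subject difference of the two heat effects. This gives 10 contrasts per pair.
3. Take the p-value from the exact sign-flip test on those contrasts (1,024 patterns), at 0.05/3.
4. Report the interval from inverting that test, or a 9-df t interval, at the matching level. Drop plain bootstrap SEs and percentile limits.
5. State that the subject is the resampling and permutation unit, and that these methods assume roughly symmetric contrasts, which exchangeable patches give under the null.

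Cost: SAP wording and minor programming, with no new data. Intervals become about 22% wider at 95% (2.262/1.859) and 29% wider at 98.33% (2.933/2.271), which is the width that 10 subjects support when the contrasts are roughly normal.

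### The secondary time-by-heat analysis in 7.3 is estimable only on reduced degrees of freedom, and it gives between-procedure contrasts, not the intra-procedure effects it states

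*Combined protocol and SAP*

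**What the plan says.** All references are to the combined protocol and SAP unless stated.

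- **Design (Protocol Summary; section 4).** For each product, "there will be two procedure days, and on all procedure days the patches will be applied for 19 hours". On Days 1, 3 and 5 the "patch will be applied without heat for 11 hours, then a theratherm® heating pad will be applied over it" for one hour. On Days 2, 4 and 6 the "patch will be applied without heat for 18 hours, then a theratherm® heating pad will be applied over it" for one hour. No session is unheated throughout.
- **Sampling (section 7.2).** Blood is drawn "15 min before patch application and then at 1:00, 10:00, 10:55, 11:05, 11:15, 11:25, 11:35, 11:45, 12:00, 13:00, 14:00, 16:00, 17:00, 17:55" and then at "18:05, 18:15, 18:25, 18:35, 18:45, 19:00 20:00, 21:00 and 22:00 hr post-patch application". That is 15 + 9 = 24 draw times, the same in every session.
- **Primary model (section 7.3).** Time enters as indicator variables, with patch, "application of heat (yes or no), and interaction between patch and application of heat". The yes/no heat variable is not defined further, and no procedure term is listed.
- **Secondary model (section 7.3).** Here "the ANOVA will also include interaction terms of time with patch and heat, and a three-way interaction between time, heat, and patch". The stated aim is the effect of heat and time within a patch, and the stated output is: "Testing the time-by-heat interaction, separately for each patch, using the same procedure outlined above produces estimates of intra-procedure effects".

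**The concern.** A time-by-heat interaction asks whether the heat effect changes over time. That needs heated and unheated records at the same time point. Within one session each clock time has exactly one heat state, so the session cannot separate heat from time. The information comes from setting the early-heat day beside the late-heat day of the same patch. Even then, many time-by-heat combinations never occur.

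Two things are at stake. First, the degrees of freedom implied by the written model are not those that the data support, and the number depends on a heat coding that the plan leaves open. Second, procedure days are at least two weeks apart. A contrast between them carries day-to-day variation, so calling it an intra-procedure effect would present between-day differences as a change seen within a session.

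**Working it through.** The plan states no df for this analysis, so there is no figure to reproduce. I count what the design supports.

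**Inputs.** 24 draw times (7.2); 2 sessions per patch, heated at 11–12 h or 18–19 h (section 4); 3 patches; time categorical and heat binary (7.3). *Assumption:* time means the 24 draws.

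**Step 1: filled cells.** Let *b* be the number of draw times at which both heat states occur across the two sessions, and *s* = 24 − *b* the rest. The full secondary model has one parameter per time × heat × patch cell, so:

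- nominal columns = 24 × 2 × 3 = 144
- rank = filled cells = 3(*s* + 2*b*)
- time-by-heat df = *b* − 1 (nominal 23)
- three-way df = 2(*b* − 1) (nominal 46)

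| Coding of heat | *b* | *s* | Rank | Time-by-heat df | Three-way df |
|---|---|---|---|---|---|
| Pad on, 12:00 and 19:00 counted as heated | 12 | 12 | 3(12 + 24) = 108 | 11 | 22 |
| Pad on, 12:00 and 19:00 counted as unheated | 10 | 14 | 3(14 + 20) = 102 | 9 | 18 |
| Any time after heat onset | 11 | 13 | 3(13 + 22) = 105 | 10 | 20 |
| Session received heat | 0 | 24 | 3 × 24 = 72 | 0 | 0 |

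Under the first coding the 12 two-state times are the six draws from 11:05 to 12:00 and the six from 18:05 to 19:00. Under after-onset coding they are the 11 draws from 11:05 to 17:55. Four earlier draws are then unheated in both sessions, and nine later ones are heated in both. A numerical rank calculation on the design matrices agrees with every row.

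**Step 2: one patch, pad on.** 48 columns, rank 12 + 24 = 36. Time plus heat takes 25, leaving 36 − 25 = 11 df.

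**Step 3: one session.** Time plus heat has 25 columns and rank 24. Time alone also has rank 24. Heat adds nothing.

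**Step 4: what the heat effect at 11:05 is.** I computed generalised least squares weights for one patch under pad-on coding. With no procedure term they are +1 on the early-heat day's 11:05 draw, −1 on the late-heat day's 11:05 draw and 0 elsewhere. The estimate uses no other draw from its own session.

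Now let a subject-by-procedure variance be *k* times the residual variance (assumed; the documents give none). The other draws of the early-heat session then receive total weight −*sk*/(*sk* + 1):

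- *k* = 1: −12/13 = −0.923
- *k* = 4: −48/49 = −0.980

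The late-heat session mirrors this. The estimate becomes the change within one session relative to the change within the other.

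**Step 5: which draws serve as the reference.** Under pad-on coding the 12 single-state draws are 4 before either window, 5 from 13:00 to 17:55 and 3 from 20:00 to 22:00. On the early-heat day 5 + 3 = 8 of the 12 follow heating, yet they count as unheated. If the model uses after-onset coding and only draws up to 17:55, *s* = 4 and all four reference draws precede heat. The weights are −4/5 = −0.80 (*k* = 1) and −16/17 = −0.941 (*k* = 4).

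**Step 6: why 18:05 to 19:00 differs.** There the comparator is the early-heat day, whose pad came off at 12:00. Section 4 gives a half-life of about 24 h. If any excess from heating decayed as a single exponential, 2^(−6/24) = 0.84 of it would remain at 18:00. Faster initial distribution would leave less. The point is that this comparator cannot be assumed unheated.

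**The case against.** The strongest reply is that the analysis works once read sensibly, and much of that stands.

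- A reader might infer that the model cannot be fitted. The documents do not support this. It is rank-deficient, but the in-window heat contrasts, the per-patch test and the three-way test are estimable on the reduced df. Under pad-on coding the empty cells lie where the two sessions share one heat state, so no in-window contrast is lost.
- A reader might infer that the F tests depend on software defaults. For the tests that 7.3 names, they do not. Each is the highest-order term in its model, so its sum of squares is unique. It is the same under treatment, sum and Helmert coding, given a proper rank tolerance. What stays open is the heat definition, which changes the df.
- A reader might infer that patches go uncompared because each is tested separately. The primary patch-by-heat test and the three-way term both compare patches. The primary model has full rank (29 of 29) under the time-varying codings.
- A reader might infer that the design holds no within-session information. Step 4 shows that a within-procedure change relative to the other procedure is recoverable, but it needs a term that 7.3 does not list.
- Coding heat as early versus late session would give full rank (144). That is a session label, not the yes/no heat variable specified.
- If time meant the five non-overlapping PK intervals in 7.2, pad-on coding would give 1 df for time-by-heat and 2 for the three-way term. The size changes, but empty cells remain.

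**Conclusion.** The secondary analysis does not have the property that 7.3 states. Under pad-on coding, 144 − 108 = 36 coefficients cannot be estimated and the df are 11 and 22. Under after-onset coding, 144 − 105 = 39 cannot, and the df are 10 and 20. As written, with no procedure term, each estimable heat effect is a within-subject, between-procedure difference that includes day-to-day variation.

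The rank and df figures rest on time meaning the 24 draws, and pad-on figures of 11 and 22 on counting 12:00 and 19:00 as heated. The amount of day-to-day variation is unknown, because the documents give no variance components. The aliasing of heat with time within a session depends on none of these assumptions. The point concerns a secondary analysis and should be corrected. It does not show that the primary model fails.

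**What to change.** 1. Define heat as time-varying and name the estimable contrasts. For the 11 draws from 11:05 to 17:55, compare the early-heat day with the not-yet-heated late-heat day of the same patch and subject at the same clock time.
2. Remove day-to-day variation from that contrast, either with a subject-by-procedure term in a model limited to draws up to 17:55, or by subtracting each session's own 10:55 draw. A raw early-minus-late difference would keep the between-day noise.
3. Compare patches through the estimable part of the three-way term, that is, differences between patches in these contrasts.
4. Report 18:05 to 19:00 separately, and say that its comparator was heated earlier.
5. State the actual df. With after-onset coding and the 15 draws up to 17:55, these are 11 − 1 = 10 for time-by-heat per patch and 2 × 10 = 20 for the three-way term.
6. Replace the intra-procedure label with *within-subject, between-procedure effects*, or with *within-procedure change relative to the other procedure* where step 2 is applied.

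The cost is SAP wording and code, with fewer stated df. No new data are needed. The separate SAP already combines the unheated portions of the early- and late-heat designs to build its IVIVC baseline (Approach II and III, step 1).
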